13.1. Description of statistical methods

Missing data handling

The missing processes was described by Rubin (1987) who made a distinction between (a) Missing Completely At Random (MCAR), (b) Missing At Random (MAR), and (c) Missing Not At Random (MNAR)¹. We will test with the statistical test of Jamshidian and Jalal (2010), implemented in the MissMech R Package (Jamshidian et al., 2014), whether missing data were MCAR. If they are not MCAR, we will investigate whether or not the missing mechanism could be explained by baseline characteristics (eg, sociodemographic, medical features) of patients using logistic regression, which would suggest an MAR mechanism. If missing data are not MCAR or MAR, they will considered as MNAR. As indicated by Molenberghs et al. (2008) one can never totally exclude a MNAR process, but every MNAR model has an MAR counterpart with equal fit. Therefore, in case of MCAR, MAR, or MNAR missing processes, maximum likelihood (ML) and multiple imputation (MI) were used, using the mice R package for the last one (Raghunathan et al. (2001) ; van Buuren & Oudshoorn (2016)) with a predefined seed. Indeed, ML and MI use all available data in the study and produce unbiased estimates of the treatment effect and correct P values. MI is also a method of choice because it allows not only to impute missing values on the outcome but also on the covariate (Dziura, 2013) and is valid for MCAR, MAR, and MNAR. (Molenberghs et al. (2008)) Molenberghs and Kenward (2007) recommended ML estimation without imposing a structure on the covariances among the repeated measures.

Analysis of primary outcomes

The primary outcomes will be analysed by a set of Wilcoxon-Mann-Whitney tests, but complementary tests will be done using mixed models for ordinal data (Hedeker & Gibbons, 2006) to take the multicenter nature of this trial into account. It is likely that patients in the same centre will tend to have correlated outcomes, meaning that they are more similar to other patients recruited within the same centre that to patients: same clinical care paths within centres will be observed, medical centre having their own medical practice preferences, and, therefore, the independence assumption underlying classical statistical tests is likely to be violated. We will therefore take this correlation between the patients of a same centre into account by using mixed models with the centre included as random effect for continuous outcomes (Chu et al., 2001; Kahan &

¹ (a) Missing Completely At Random (MCAR): the missingness pattern is independent from observed and unobserved data; (b) Missing At Random (MAR): conditional on the observed data, the dropout is independent of the unobserved measurement; and (c) Missing Not At Random (MNAR): when neither MCAR nor MAR hold, the missingness depends on the observed, as well as on the unobserved data.

Morris, 2013) and mixed models for discrete data will be used to model binary outcomes (Kahan & Harhay, 2015).

For demographic and baseline data, continuous data will be compared by means of T-test when homogeneity of variances, tested with the Bartlett's test, and normality of the residuals, tested with the Shapiro-Wilks test, will be reached and means and standard deviations (means \pm StDev) will be reported. When homogeneity of the variance or normality of the residuals won't be proved, Wilcoxon signed rank test will be performed on rank data and medians and inter-quartile ranges (median [Q₂₅ - Q₇₅]) will reported. For count data, the Pearson Chi-Squared test will be performed to compare proportions. We will use the software R, version 3.6.2 or above (R Core Team, 2017) to perform the statistical analyses.

Hedeker D, Gibbons RD (2006). Longitudinal Data Analysis. Wiley-Interscience, Hoboken, NJ.

Kahan, B.C. & Haray, M.O. (2015). Many multicentre trials had few events per centre, requiring analysis via random-effects models or GEEs. Journal of Clinical Epidemiology, 68(12), 1504-1511.

Kahan, B.C. & Morris, T.P. (2013). Analysis of multicentre trials with continuous outcomes: when and how should we account for centre effects? Statistics in Medicine, 32(7), 1136-1149.

Rubin DB. Inference and missing data. *Biometrika*.1976;63:581–592.

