4. CLINICAL INVESTIGATION SUMMARY

Title	Comparative study 27G to larger gauge vitrectomy		
Reference Number (Acronym)27G compared to larger gauge sizes			
Clinical Phase	Post-Market stage		
Objectives	To perform a prospective randomized comparison of postoperative recovery between 27G and larger gauge surgical approaches		
Endpoints	Primary endpoint: determine whether ultra-small gauge surgery (27G) improves postoperative outcome and patient morbidity		
Design	Investigator-initiated, comparative double-arm, mono-center, prospective, interventional case study		

Data Collection	Total duration of study for each patient will be 1 week or less (from surgery to last follow-up). See Study Flow Chart 7.3
Planned Clinical investigation Period	2020-2021
Clinical investigation population	Patients that are scheduled for a vitrectomy surgery for either floater removal or macular surgery, with or without combined cataract (phaco) surgery.
Number of Participants	Target 500 patients
Inclusion/Exclusion Criteria	 Inclusion criteria Patients aged over 18 No prior vitrectomy surgery in the study eye (for the same eye) No prior inclusion in this trial Scheduled for vitrectomy for floater removal or macular surgery (including macular holes) without endotamponades such as PFCL, Gas or Silicone oil. Air tamponade is allowed. Exclusion criteria Patients with serious heart, lung, liver, or kidney dysfunction Patients with proliferative diabetic retinopathy, endophthalmitis, uveitis, eyes with refraction >+5D or <-8D, or other eye disease that impacts the outcome of vitrectomy surgery Patients with history of drug abuse or alcoholism Patients participating in other drug or medical device clinical trials before screening for this trial Pregnancy, preparation for pregnancy during clinical trial, or breast-feeding Belief by the investigator that a patient's condition would hinder the clinical trial, such as a patient prone to mental stress, loss of control of mood, or depression
Device Name	EVA used in combination with a trocar system, light fiber, vitrectome and laser fiber either in 27G or larger gauge sizes. In case of a combined surgery also a phaco hand piece and phaco needle are used.
Principle Intended Use	All devices are used within their claimed intended use. In general, all devices are intended to be used during ophthalmic surgery.
Manufacturer Name	D.O.R.C. Dutch Ophthalmic Research Center (International) B.V.

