11. CLINICAL INVESTIGATION ASSESSMENTS

11.1. Subject Characteristics

The following parameters will be collected:

- 1. History: prior eye surgery (excluding previous vitrectomy)
- 2. Surgical parameters:
 - Indication of the surgery
 - Anesthesia type: local / general / local with sedation / general with parabulbar
 - Technique: 23G, 25G or 27G
 - Combined phacovitrectomy: yes / no If yes: Phaco power used: Total phaco time, effective phaco time and average phaco power
 - Surgery time:
 - \circ $\;$ total time of surgery
 - $\circ \quad \text{phaco time} \quad$
 - \circ vitrectomy time
 - peeling time
 - Tamponade(s) used (only air allowed)
 - Diathermy applied (Yes/No)
 - Phaco femto applied (Yes/No)
 - Cryo applied (Yes/No)
 - Laser applied (Yes/No)
 - Vital dyes used: yes/no If yes: type:
 - ILM peeling performed: yes/no

PVD created: yes/no

- Vitreous stain used: yes/no If yes: Type:
- Anticoagulants used by subject: recorded in the eCRF in list of concomitant medication(s):
 - Yes/No
 - o Type
 - Stopped: Yes/No
 - Time stopped
- Medications used:
 - Preoperative disinfection:
 - Preoperative preparation (dilation drugs):
 - $_{\odot}$ $\,$ Infusion liquid use:
 - Additives in infusion liquid:
 - Intra-operative: intra-cameral or intravitreal medication
 - Postoperative:
 - Parabulbar:
 - Topical:
 - General:
- Actions required to close the eye at the end of the surgery
 - o None
 - Sclerotomy massage
 - Sclerotomy squeezing
 - $\circ \quad \text{Injection of air bubble}$
 - \circ Suturing of the sclerotomy
 - If yes: number of sutures placed
- Adverse events during surgery^{6,7,8,9}:
 - Phaco:
 - Zip in capsulorhexis
 - Posterior capsule tear
 - Vitreous prolapse
 - Iris prolapse
 - Dropped nucleus
 - Vitrectomy:
 - o Iatrogenic retinal tear
 - Lens touch
 - o Choroidal hematoma
 - Infuse subchoroidal
 - Iatrogenic retinal damage
 - Subretinal haemorrhage
 - o Iris trauma
 - Retinal incarceration
 - PFCL subretinal
 - Oil subretinal
 - Hemorrhage from retinal vessel
 - Hemorrhage from choroid
- 3. Postoperative parameters:
 - Amount of pain during the first 24 postoperative hours (using pain scale)
 - Visual acuity day 1 postoperative

- Intra-ocular pressure day 1 postoperative
- Slit-lamp examination day 1 postoperative: flare and cells in the anterior chamber
- Photograph of the external eye to assess reddishness and swelling of eyelids

[figure not shown]
4. Questionnaire

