11.3. Surgical procedure

The patient will be operated under local anesthesia, local anesthesia with sedation or general anesthesia, depending on the surgeon's and patient's preferences and general status of health. In the patients is phakic, the surgery may be combined with a cataract surgery (phaco-emulsification). As in the standard of care in each surgical center, the patients may stay overnight in the hospital after the surgery or can be treated on an outpatient basis.

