13. STATISTICS

General comment: for the statistical analysis, a comparison will be made between both study arms included *in each center*. Hence, there will only be a comparison between both study arms in each site. No pooling of the data from the different sites will be performed nor will there be a comparison between the different study sites.

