13.2. The number of participants

We estimated the number of participants by calculating the number of participants needed for the three chosen outcomes (bio cellen, bio tyndall and redness of the eye), based on the pilot data. The target p-value was 0.5/3 (=0.0167) in order to correct for multiple testing, and the power was set to 80%. Because we want to see a difference on the three outcomes, we choose the highest sample size estimation, based on the work of Zaho, Rahardja & Yongming (2008), who proposed sample size estimators ordinal data using the Wilcoxon-Mann-Whitney test and available in the R package *sample size*. The percentages for each categories of the ordinal variables by group are used as input for the sample size estimations. The next table presents the results obtained.

	Total by group	Total individuals
Bio cellen	428	858
Bio tyndall	430	860
Redness eye	27	54

Based on this table, a total of 860 patients would be required by group in order to show a difference between 23G and 27G on the three parameters of the outcome: bio tyndall, bio cellen and redness eye.

For each surgical site 25 patients will be recruited by group (i.e. 50 patients will be included at each site).

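### Does leaving combined phaco out of the primary tests and the mixed models undermine the 25 v 25 comparison at each site?

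*Combined protocol and SAP*

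**What the plan says.** Section 4 admits patients for vitrectomy "with or without combined cataract (phaco) surgery". Section 11.3 adds that in phakic eyes "the surgery may be combined with a cataract surgery (phaco-emulsification", at no fixed rate. Section 11.1 lists "Combined phacovitrectomy: yes / no" among the surgical parameters, so the recorded item is phaco as performed.

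Section 13.2 sizes the trial on "three chosen outcomes (bio cellen, bio tyndall and redness of the eye". Section 11.1 grades flare and cells in the anterior chamber on day 1. On site size, section 13.2 says: "For each surgical site 25 patients will be recruited by group".

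For the analysis, section 13.1 says: "The primary outcomes will be analysed by a set of Wilcoxon-Mann-Whitney tests". It adds complementary ordinal models and speaks of "mixed models with the centre included as random effect". No other model term is named. Section 13 opens with the rule "No pooling of the data from the different sites will be performed". Section 9.3 provides a 25:25 list with no stratification factor and lets the surgeon see the arm just before surgery. Section 13.5 lets covariates that predict missingness into the model. Section 13.6 leaves the final statistical plan to be agreed before data lock.

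**The concern.** Phaco is performed in the anterior chamber, where two of the three sizing outcomes are graded. It is therefore natural to suspect that it affects them. Fifty patients are few enough for the arms at one site to differ noticeably in phaco share. Because sites are not to be pooled, other sites cannot average out such an imbalance.

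If phaco were strongly prognostic, a site with an uneven split would have a raised chance of a false difference between gauges. Readers would also find that site's result hard to interpret. A Wilcoxon test stratified by phaco (van Elteren), or a phaco term in the ordinal model, seems an inexpensive safeguard, and section 13 contains neither.

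**Working it through.** **The plan's own figures.** Section 13.2 prints the per-outcome level as 0.5/3 (=0.0167). The value 0.0167 is 0.05/3, and that is used here, two-sided as in section 13.3. The table gives 428, 430 and 27 per group for cells, flare (tyndall) and redness. Doubling gives 856 (858 printed), 860 and 54. The sample sizes cannot be rederived because the pilot percentages are not printed.

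**Power at one site, from those sizes.** Power = Φ[(2.394 + 0.842) × √(50/N) − 2.394], where N is the total that gives 80% power.
- Flare, N = 860: 3.236 × 0.2411 − 2.394 = −1.614, so power is 5.3%. Cells give the same.
- Redness, N = 54: 3.236 × 0.9623 − 2.394 = 0.720, so power is 76%. Simulating the actual test gives about 80%.

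**Chance of imbalance.** The phaco share is not in the documents; 30% to 70% is assumed. Taking the difference of two Binomial(25, p) counts, the probability of a gap of at least five patients is 16.4% at p = 0.3, 19.3% at 0.4 and 20.3% at 0.5. It is symmetric above 0.5, and only 3.4% at p = 0.1. If ten sites fill (500/50), the chance that at least one is this uneven is 1 − (1 − 0.164)^10 = 83% to 1 − (1 − 0.203)^10 = 90%. Imbalance somewhere is therefore likely.

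**Consequence of imbalance.** One site was simulated at 25 v 25, with a five-grade proportional-odds outcome (control arm 20% per grade), level 0.0167, and at least 40,000 sites per setting. The treatment effect was set so that the ties-adjusted formula returns 430 or 27 per group. The phaco odds ratio (OR) is assumed to be 1 to 4. Planned and performed phaco are assumed to disagree in 0% to 20% of patients, because only planned status could safely define strata. Each cell shows the unstratified then the stratified test.

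| Phaco OR | Disagreement | False positives at uneven sites, share 30% | share 50% | Redness power, share 30% | share 50% |
|---|---|---|---|---|---|
| 1 | 0% | 1.5–1.7% for both | 1.5–1.7% for both | 79.7 / 78.2% | 79.7 / 78.3% |
| 2 | 0% | 2.04 / 1.61% | 1.93 / 1.58% | 79.8 / 79.6% | 79.6 / 79.7% |
| 2 | 20% | 2.10 / 1.83% | 2.05 / 1.75% | 79.9 / 78.8% | 79.8 / 79.0% |
| 4 | 0% | 3.09 / 1.55% | 2.94 / 1.50% | 80.1 / 84.2% | 79.8 / 84.9% |
| 4 | 20% | 3.26 / 2.38% | 3.11 / 2.32% | 79.5 / 79.9% | 79.9 / 81.0% |

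Over all sites, both tests gave 1.45% to 1.61%. Flare power was 4.8% to 5.3% unstratified and 4.7% to 5.5% stratified.

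**Reconciling the conditional and overall rates.** At share 50%, OR 4 and no disagreement, uneven sites contribute 0.203 × 2.94% = 0.60 points. The remaining 79.7% of sites must then run at (1.45 − 0.60)/0.797 = 1.1% to (1.61 − 0.60)/0.797 = 1.3%, below nominal. The excess at uneven sites is offset elsewhere.

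**Size over the trial.** With ten sites and one outcome, the extra false positives at uneven sites without stratification are 10 × 0.203 × (0.0294 − 0.0150) = 0.029 at OR 4. At OR 2 they are 10 × 0.203 × (0.0193 − 0.0158) = 0.007.

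**The case for a change.** The best case for adjusting is that a reader of one site's result cares about the error rate given the imbalance seen there, not the average over imbalances that did not occur. Without pooling, that site stands alone. A covariate named in advance cannot be called selective, whereas one added after an imbalance is found can. Stronger phaco effects than those above would also matter more. In a separate simulation (6,000 runs per setting, arm log odds ratio fixed at 1.5), a phaco log-odds effect of 2 (OR about 7.4) gave 3.9% to 4.6% false positives at uneven sites unstratified, and 1.1% to 1.3% stratified. Power was 50% to 52% against 64%.

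The preference for conditional error control stands, and so does the value of deciding beforehand. The rest carries less weight:
- Effects that large have no support in the documents. Nor do the documents say that phaco matters more than indication, ILM peeling or anaesthesia, all of which are also recorded. The argument fits any of them.
- The anterior-chamber rationale applies to cells and flare, where a single site has about 5% power with either test. Redness is the one outcome with usable power, and the documents give no reason to expect phaco to affect it. If phaco does not, stratifying costs about 1.5 points.
- Section 11.1 lists phaco as performed, and the surgeon knows the arm beforehand (section 9.3). Performed phaco is therefore not guaranteed to be a pre-randomisation variable. A sound adjustment needs planned status fixed before allocation in each centre's separate database (section 12.3), possibly with an amendment (section 16.1).
- A phaco term in a mixed model across centres belongs to a pooled analysis, in which single-site imbalances do average out. That model conflicts with the no-pooling rule in section 13. The conflict is real, but it is a separate and larger matter.

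**Conclusion.** The concern does not hold as a fault in the plan. Phaco is indeed absent from section 13, but randomisation keeps the unadjusted Wilcoxon test at its nominal level, and no passage requires or promises adjustment. Stratifying leaves overall type I error and the power for cells and flare essentially unchanged. At odds ratios 1 to 2 it moves redness power by about -1.5 to +0.1 points. It clearly helps only at the 16% to 20% of sites that are uneven, with an odds ratio near 4 and close agreement between planned and performed phaco: there the rate falls from about 3% to 1.5%.

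These sizes rest on an assumed phaco share of 30% to 70%, odds ratio of 1 to 4 and disagreement of 0% to 20%, none of which the documents give. Experienced statisticians could choose either way. Section 13.6 leaves the choice open until the final statistical plan is agreed.

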9.3. Randomisation

A 25:25 patient randomization list will be generated in the eCRF (RedCap) to determine whether the surgery will be performed using 27G or larger gauge instruments. This randomization list will be masked for the surgeon: only prior to the next patient scheduled for surgery, the study arm will be visible for the surgeon since the difference in size will be visible during surgery.

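### If the primary Wilcoxon-Mann-Whitney tests are to give a result over sites, they should be stratified by site, and section 13 must first allow such a result

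*Combined protocol and SAP*

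**What the plan says.** On the test, section 13.1 reads "The primary outcomes will be analysed by a set of Wilcoxon-Mann-Whitney tests, but complementary tests will be done using mixed models for ordinal data", with no mention of stratification. Site enters only in the second tier, the mixed models, with centre as a random effect. The reason given there is that patients at one centre resemble each other, so that "the independence assumption underlying classical statistical tests is likely to be violated".

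On the level of comparison, the general comment that opens section 13 says "Hence, there will only be a comparison between both study arms in each site" and "No pooling of the data from the different sites will be performed". The introduction (section 5) and section 12.3 say the same, and 12.3 gives each centre its own database.

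On allocation, section 9.3 sets up a 25:25 list and section 13.2 adds "For each surgical site 25 patients will be recruited by group". With one database per centre, this amounts to balanced randomisation within site.

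On size, section 8.1 gives one total of 500, with at most 50 at any site. The table in 13.2 requires 428 per group for cells (bio cellen), 430 for flare (bio tyndall) and 27 for redness.

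**The concern.** The plan points two ways. The general comment describes a series of separate 25 v 25 comparisons. A centre random effect cannot be fitted to one centre, and 430 per group has no meaning for a site with 25 per group, so 13.1 and 13.2 describe a result over sites.

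If there is a result over sites, the named primary test does not match the design. An ordinary rank test on all eyes ranks patients from one site against patients from another, so differences between sites count as noise, although the within-site balance has already removed them from the treatment comparison. The test remains valid but becomes conservative, and it loses power on cells and flare, the two outcomes where the planned 500 patients are already short.

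**Working it through.** **Inputs.** Alpha 0.0167 per outcome, two-sided, and power 80% (13.2, 13.3). Per-group sizes 428, 430 and 27 (table in 13.2). Sites of 25:25 (9.3, 13.2) and a total of 500 (8.1), hence ten sites if all fill. Redness has five grades (Appendix A). The documents give no ICC; 0 to 0.3 is assumed here.

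**The plan's own figures.** The sample sizes cannot be reproduced, because the pilot category percentages are not printed. The arithmetic around them can be checked:
- 0.05/3 = 0.0167, as used; the printed 0.5/3 would be 0.1667.
- 2 x 430 = 860 and 2 x 27 = 54 match the table; 2 x 428 = 856, against 858 printed.
- The sentence below the table calls 860 a per-group number, but the table has it as the total. The table is used here.

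**Step 1: power at one site and over all sites.** Scaling from the stated size n0,

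power(n) = Phi[(z_a + z_b) x sqrt(n/n0) - z_a], with z_a = 2.394 and z_b = 0.842, sum 3.236.

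- Flare, 25 per arm: 3.236 x sqrt(25/430) - 2.394 = 0.780 - 2.394 = -1.614, power 5%. Cells (n0 = 428) give the same.
- Flare, 250 per arm: 3.236 x sqrt(250/430) - 2.394 = 2.467 - 2.394 = 0.073, power 53%.
- Redness, 25 per arm: 3.236 x sqrt(25/27) - 2.394 = 3.114 - 2.394 = 0.720, power 76%. At 250 per arm it is practically 100%.

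**Step 2: ordinary against site-stratified test over sites.** Simulated trials had ten sites of 25:25, a latent normal outcome cut into five equally frequent grades, a random site effect and one common treatment effect. The shift was 0.235 within-site SD, which gives 80% power at 430 per arm under the ties-adjusted formula that 13.2 cites. Both tests were applied to the same data. The van Elteren statistic is

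sum of w_k (W_k - E[W_k]) / sqrt(sum of w_k^2 Var[W_k]), with w_k = 1/(n_k + 1),

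where W_k is the rank sum within site k and n_k is the number of patients there. There were 10,000 runs per row.

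| ICC | Ordinary | Stratified | Difference (points) |
|---|---|---|---|
| 0 | 53.7% | 53.4% | -0.3 |
| 0.02 | 52.8% | 53.2% | 0.4 |
| 0.05 | 51.0% | 52.8% | 1.8 |
| 0.10 | 48.8% | 52.7% | 3.9 |
| 0.20 | 42.9% | 51.6% | 8.7 |
| 0.30 | 36.3% | 50.2% | 13.9 |

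With three grades the differences are somewhat smaller: 1.1, 3.2, 7.6 and 12.8 points at ICC 0.05, 0.1, 0.2 and 0.3. The pattern is the same.

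**Step 3: type I error (nominal 1.67%, 20,000 runs).** The ordinary test gives 1.5% at ICC 0, 1.2% at 0.1 and 1.0% at 0.2. The stratified test stays between 1.5% and 1.7%.

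**The case against.** The strongest reply is that the plan contains no test over sites. The general comment governs the whole of section 13, and under it each Wilcoxon-Mann-Whitney test uses one site's patients, so there is nothing to stratify. This stands as a limit. A reader might infer from 13.1 that the primary test simply ignores site; the documents do not support that, because section 13 confines comparisons to single sites. The loss arises only for a result over sites, which 13.1 and 13.2 imply and the general comment excludes.

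Second, site is already handled in the complementary models. That is true, so what remains is which site-aware analysis is primary. Nothing here shows van Elteren to be better than the ordinal mixed model, and either would do.

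Third, the size rests on an assumed ICC and almost vanishes at 0.02. It also depends on the scale of the pilot effect, which the plan does not give. The table holds the effect fixed in within-site SD. Held fixed in total SD, the ordinary test stays just above 50% and the stratified test rises to about 67% at ICC 0.3. A gap remains, but as a gain forgone rather than a fall in power.

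Two further readings are tempting and unsupported. One is that the plan fears a liberal test and has the direction wrong: 13.1 names no direction. The other is that its error bars are too wide: the plan specifies no interval for the rank test.

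**Conclusion.** The point holds in conditional form. The first matter to settle is the conflict between the general comment in section 13 (with 12.3) and the analysis and sample size in 13.1 and 13.2. If only per-site tests are meant, power of about 5% for cells and flare is a far larger problem than missing stratification. If a result over sites is meant, an unstratified primary test does not follow the within-site randomisation. It then costs about 1 to 2 power points at ICC 0.05, 4 at 0.1, 8 to 9 at 0.2 and 14 at 0.3, while stratifying costs practically nothing at ICC 0. Redness keeps practically full power over sites.

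These figures assume a common effect and ten full sites, whereas 8.1 sets 50 per site only as a maximum. There is no added false-positive risk. This is a cheap improvement rather than an error that invalidates the trial.

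**What to change.** 1. In the general comment of section 13, and in section 12.3, say whether a result over sites is intended. If it is, reword the ban on pooling so that within-site comparisons may be combined into one statistic.
2. In 13.1, state that the primary over-site test of each of the three outcomes is the site-stratified Wilcoxon (van Elteren) test, or else that the planned centre-adjusted ordinal model is primary. Choose one, before data lock, in the final statistical plan that 13.6 foresees.
3. Keep the ordinary Wilcoxon-Mann-Whitney test for a single site's own result.

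The cost is a few sentences and a few lines of R, with no new data. Van Elteren needs only each site's rank sum, its variance and the site size, so the separate databases could remain; the mixed model needs patient-level data brought together.

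The real downside is a change in the plan's stated scope. One trial-wide p-value averages over sites whose comparator is 23G or 25G, so the per-site results should still be shown beside it.

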6. OBJECTIVES

6.1 Primary objective

The primary objective and primary endpoint are shown in the table below:

Primary objective	Primary endpoint
The aim of this study is to perform a prospective randomized comparison of postoperative recovery between the 27G and larger gauge surgical approach. Patients will be randomized to be operated using 27 gauge or a larger	The outcome of the trial is to prospectively determine whether ultra- small gauge surgery (27G) improves postoperative outcome and patient morbidity.
gauge size.	 For this purpose, the following postoperative parameters will be used: Post-operative redness (Eye Photo) Ophthalmic examination including biomicroscopy to evaluate the amount of intra-ocular inflammation.

The secondary objective and secondary parameters are shown in the table below:

Secondary objective	Secondary endpoint
To obtain additional outcome parameters for both the 27 gauge and larger gauge surgery	Postoperative parameters: - Visual Acuity (LogMAR BCVA) - Intra-ocular pressure (mmHg) - Pain assessment (Questionnaire with visual analogue scale)

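### Section 13.1 names a paired test (Wilcoxon signed rank) as the fallback for comparing continuous demographic and baseline data between two independent arms

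*Combined protocol and SAP*

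**What the plan says.** Section 13.1 (Description of statistical methods) gives a rule for baseline comparability: "For demographic and baseline data, continuous data will be compared by means of T-test", provided that Bartlett's test and the Shapiro-Wilk test support equal variances and normal residuals. The fallback follows: "When homogeneity of the variance or normality of the residuals won't be proved", the "Wilcoxon signed rank test will be performed on rank data", with medians and quartiles reported. The rule does not say whether the t-test is paired or unpaired.

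The design is parallel-group. Section 6.1 states: "Patients will be randomized to be operated using 27 gauge or a larger" gauge size. Section 9.2 allows only one eye per patient. Section 9.3 states: "A 25:25 patient randomization list will be generated in the eCRF (RedCap"), and Section 13.2 gives 25 patients per group at each site.

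For outcomes, Section 13.1 names other methods. "The primary outcomes will be analysed by a set of Wilcoxon-Mann-Whitney tests", with ordinal mixed models as a complement. It also names "mixed models with the centre included as random effect for continuous outcomes", and mixed models for discrete data for binary outcomes.

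**The concern.** The signed rank test works on within-pair differences, or on one sample against a fixed value. To use it on two arms, each 27G patient must be matched to one larger-gauge patient. Nothing in the design supplies that match: there are no fellow eyes, no repeated measures used for this purpose, and no matched pairs. An analyst who follows the sentence literally would have to pair patients by their order in the data file.

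This is a stated rule that is wrong, not a detail left open. Within the same section, the primary outcomes get a differently named and correct test, so the text gives no signal that the two names mean the same thing. At stake are the p-values in the baseline comparability table for any continuous variable that fails the pre-tests.

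**Working it through.** No sample size, power or alpha in the plan depends on this test, so there is no stated figure to reproduce. The check has two parts.

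**1. Test against design.**
- Structure that the signed rank test needs: n pairs (x_i, y_i), hence equal counts and a meaningful index i.
- Structure that the design gives: two separate groups of patients, one eye each (Sections 6.1, 9.2 and 9.3). There is no index i that links a patient in one arm to a patient in the other.
- Equal counts are not assured. Section 8.1 sets up to 50 per site, and Section 9.4 allows withdrawal. With 25 against 24 values, the paired routine stops with an error.

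**2. Consequence when the counts are equal (simulation).**

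From the documents: 25 per arm (Sections 9.3 and 13.2) and a two-sided 5% level (Section 13.3).

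Assumed: independent lognormal data with log-scale SD 1. Skewed data of this kind are what the normality check is meant to send to the fallback. The pre-tests themselves were not simulated. The log-scale shift is 0 for type I error and 0.8 SD for power. There were 10,000 runs, and pairing was by row order.

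| Scenario | Signed rank, arbitrary pairs | Rank-sum |
|---|---|---|
| No difference: rejection rate | 4.8% | 5.0% |
| Shift 0.8 SD: rejection rate | 70.6% | 76.5% |

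The Monte Carlo standard error near 5% is √(0.05 × 0.95 / 10,000) = 0.2 percentage points, so the type I error of both tests agrees with the nominal level. The power loss is 76.5 − 70.6 = 5.9 percentage points. The standard error of each power figure is under 0.5 points (√(0.706 × 0.294 / 10,000) = 0.46 points), so the loss is real under these assumptions.

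**Dependence on row order.** Three simulated data sets (25 per arm, lognormal, assumed shift 0.6 SD) were each re-paired at random 5,000 times. The data do not change; only the pairing does.

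| Rank-sum p | Signed rank p, min to max | 5th to 95th percentile | Pairings with p < 0.05 |
|---|---|---|---|
| 0.0003 | 0.0000004 to 0.007 | 0.00002 to 0.0009 | 100% |
| 0.18 | 0.004 to 0.73 | 0.06 to 0.33 | 3.5% |
| 0.17 | 0.011 to 0.92 | 0.10 to 0.49 | 0.7% |

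The rank-sum test gives one p-value per data set, whatever the row order.

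**The case against.** **The rule covers baseline data only, and little follows from it.** This stands. The plan makes no decision depend on a baseline p-value: Section 13.5 chooses covariates by their relation to missingness. Differences between properly randomised arms at baseline arise by chance under any test.

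**The p-values are not meaningless.** This also stands. A reader might infer that a paired test on unpaired arms gives worthless p-values. With arbitrary pairing the type I error stays near 5%. The minimum and maximum over thousands of pairings show the extremes; in the three data sets above, at least 96.5% of pairings fall on the same side of 5% as the rank-sum test. The accurate description is order-dependent, less powerful, and not computable with unequal counts.

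**The error might spread to secondary outcomes.** A reader might infer this because Section 13 rules out pooling across sites, while the method named for continuous outcomes is a mixed model with centre as a random effect, which cannot be fitted within one centre. The signed rank sentence would then be the only rule left for non-normal continuous data such as pain score or pressure. The documents do not support that step. They limit the sentence to demographic and baseline data and assign the signed rank test to no outcome. The conflict between no pooling and the mixed models leaves a missing within-centre method, which is a separate matter.

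**It is probably a slip of the name.** This is plausible, since the same section uses the unpaired Wilcoxon-Mann-Whitney test elsewhere, and unequal arms would expose the error at once. But no text confirms it, and the sentence as written names the wrong test.

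**Imputation would restore equal counts.** Only in part. The multiple imputation in Section 13.1 can fill missing values, but it does not add patients to a site whose arms were not equally filled. It also does nothing about the absence of pairs.

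**Conclusion.** The plan is wrong as written, with minor severity. Section 13.1 names a paired test as the fallback for comparing continuous demographic and baseline data between two independent randomised arms. The test cannot be run with unequal counts. With equal counts, its p-value changes with row order, and it loses about 6 points of power (about 71% against 77%) while keeping its type I error near 5%.

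The power and order figures rest on assumed lognormal data, assumed shifts (0.8 SD for power, 0.6 SD for the re-pairing) and 25 per arm; other distributions would move them. The mismatch between test and design rests on the documents alone.

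The stated primary-outcome tests and the sample size in Section 13.2 rest on the unpaired Wilcoxon-Mann-Whitney test and are not touched by this point.

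**What to change.** In Section 13.1, replace the Wilcoxon signed rank test with the Wilcoxon rank-sum (Mann-Whitney) test, and state that the t-test is the unpaired two-sample test.

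The cost is one sentence of wording. It needs no new data and no change to the sample size. It is best done before the final statistical plan is agreed. Section 13.6 requires later deviations to be reported, so if the sentence is carried forward, even running the correct test would have to be declared as a deviation.

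Whether to test baseline differences at all, or to keep the variance and normality pre-tests, is a separate preference and not part of this correction.
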